7. Disseminate findings for broader application by health professionals through channels of peer-reviewed publications and presentations at conferences on aging.

Statistical Analyses and Data Management

Sample size, power considerations, and statistical analysis plans are provided in full in the Study Record: the PHS Human Subjects and Clinical Trials Information document.

Project Management and Schedule

As described in the multiple PI leadership plan, Drs. [name] and [name] together will provide oversight of the entire project. Since the proposed research is interdisciplinary and involves multiple schools/departments, a governance structure will be implemented in order to ensure effective management and coordination. The proposed research will follow a work plan that will meet the milestones shown in the “Study Timeline” attached to the Study Record: the PHS Human Subjects and Clinical Trials Information document. We will hold bi-monthly general project meetings involving all staff and investigators to present the latest data and to coordinate study logistics and analysis. The team of investigators on this proposal is well-poised to integrate their various disciplines and ensure a high probability of success for accomplishing the proposed specific aims.

DATA MANAGEMENT AND STATISTICAL CONSIDERATIONS

Study Power and Analysis Plans:

With 50 subjects randomized to blocks 2 (“bedroom alone AFU”), and (“control”) in a random sequence, we anticipate adequate power using our proposed cross-over study design for observing significant reductions in **average systolic BP (primary endpoint)**. With the repeated BP measurements collected in this cross-over design, we will do paired analysis for power calculations, since each subject can serve as their own control given sufficient washout periods and because we have a priori pre-specified the group comparison hypothesis for each aim clearly beforehand. We will be able to achieve 90.3% power in **Aim 1a** for detecting a 3 mm Hg in mean systolic BP difference comparing the “bedroom AFU” to the “control” group at both the acute (4-day) and chronic (4-week) time periods, assuming that the standard deviation (SD) of systolic BP is 8.2 mm Hg. The detectable mean difference of systolic BP between “bedroom FU” vs “control” with the corresponding statistical powers that we can achieve is as follows:

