Detectable mean BP difference between “active intervention” vs. “control” (Hg)	2.4 mm	2.6 mm	2.8 mm	3 mm Hg	3.2 mm	3.4 mm
Statistical Power	75.4%	81.9%	86.1%	90.3%	93.6%	95.4%

Within the range of the SD of systolic BP measurements from 6.2 to 9.8, the statistical power for aim 1a we can achieve ranges between 72.1% and 97.5% to detect a 3 mm Hg change in mean systolic BP. Similar powers will be achieved for **Aim 2a** as well, comparing “bedroom alone AFU” (block 2) versus “control” (block 3) group. In our previous AFU study (RAPIDS, see: Progress Report) we observed a 3.2 mm Hg reduction in systolic BP by active versus control intervention. Therefore, the pre-specified effect size (3 mm Hg systolic BP reduction) for which we have designed this renewal proposal to have adequate power to observe is well justified. The study is a priori designed and

powered to determine the pre-specified outcomes in aims 1a, 2a, and 2b. Other comparisons evaluated in aims 1b (24-hr personal-PM_{2.5} exposures); 1c (secondary health endpoints); 2c (24-hr personal-PM_{2.5} exposures); 2d (secondary health endpoints); as well as in aims 3a (differences in steroid levels between blocks) and 3b (mediation analyses) are all deemed secondary study outcomes. We will collect the data as proposed and analyze the results using the same statistical methods as outlined for the primary study outcomes. However, since these are secondary endpoints only (i.e., hypothesis generating results), we will analyze the data for trends and for “nominal” statistical significance. We will also not perform a priori power calculations for all secondary endpoints.

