Both the primary endpoints and the secondary measures such as diastolic BP, 24-hour BP levels and HOMA-IR will be reported as mean (median) \pm SD (IQR). One-sample paired t-test will be performed to compare each outcome variable between active intervention group and the control group. In case there are extreme values or that the variables are not normally distributed, Wilcoxon signed-rank test, a non-parametric test for comparing repeated measurements' mean ranks, will be performed for robustness¹. When the distribution of an outcome variable is not anticipated to follow a normal distribution, we will transform it to meet normality assumptions as best as possible before we fit regression models to adjust for confounders (age, sex, BMI, dose of BP tablets, type of BP control medication). Non-parametric correlation coefficients, such as Kendall's tau⁷ or spearman's rho⁸, between the principal outcomes and exposure measures will be calculated at each time point. Such measures provide robust inferences. Multiple hypothesis testing will be adjusted through the Holm's procedure⁹.

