More specifically, to adjust for other confounders, we will use linear mixed models²⁻⁴ to evaluate the effect of interventions on the outcomes (e.g. BP levels) adjusting for confounders. The mixed models will fully represent the structure of the data by taking into account the within-subject correlations of the outcome variables measured repeatedly at different time points over the study design. We will also evaluate the impact of other variables that may impact the results. To be more specific, a mixed effect model with a random intercept and a random slope²⁻⁴ will be fit for the longitudinal measurement of the outcomes: $Y_{ij} = a_0 + a_1 t_{ij} + a_2 I(B_{ij} = 1) + a_3 I(B_{ij} = 2) + a_4 X_{ij} + b_{i0} + b_{i1} t_{ij} + e_{ij}$, where Y_{ij} denotes the repeated average BP outcomes for subject i at occasion j , B_{ij} denotes what intervention is subject i randomized to at occasion j , and X_{ij} are the other covariates that would be controlled in the model (age, sex, BMI, dose of BP tablets, type of BP control medication). So in **Aim 1a**, we hypothesize $a_2 \neq 0$ and test for $H_0 : a_2 = 0$, and in **Aim 2a**, we hypothesize $a_3 \neq 0$ and test for $H_0 : a_3 = 0$, and in **Aim 2b**, we are testing $a_2 = a_3$. Similar models will be fit for other secondary outcome variables, such as ABPM, HOMA-IR, etc. When it happens some outcome variables have inflated zero measures, we will adopt zero-inflated regression models or a two-part mixture regression (tobit) model^{5,6} on the outcome changes between “active intervention” vs. “control”.

Other statistical considerations:

Missing data: We will try to avoid missing data when collecting data through the study design. When missing data happens, we will test if the data are missing completely at random (MCAR). If it is MCAR or the amount of missing data is less than 10%, analysis will be performed based on the complete data. If the amount of missing data is more than 10%, multiple imputations (5-10 times) will be utilized through mi package in R¹⁰. The analysis will be performed on each imputed data set, and later merged through mitools package in R¹¹. Multiple imputations are based upon the missing-at-random (MAR) assumption¹². Sensitivity analysis¹³ will be examined when inferences depart from the MAR assumption.

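### Aim 1a is a 4-week claim, but the one test tied to it by name averages weeks 1 and 4, no deciding week or method is stated, and the set of three aim tests needs a third condition that the trial lacks

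*Combined protocol and SAP*

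**What the plan says.** **The aim.** Specific Aims places Aim 1a (lower resting morning BP, the primary outcome) in 4-week periods of use, within a two-way crossover of bedroom filtration against sham. The Significance section makes persistence over weeks the open question. Trial Overview gives the 4-day assessment a corroborating role.

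**The endpoint.** Table 1 lists the primary outcome as the 4-day systolic average in weeks 1 and 4, and assigns it to Aims 1a, 2a and 2b. The Protocol Modifications replace the BpTRU readings with home readings, morning and evening, and keep both weeks. They do not touch the analysis.

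**The analysis** (Study Power and Analysis Plans):

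- Power for Aim 1a is a paired calculation, claimed "at both the acute (4-day) and chronic (4-week) time periods".
- "One-sample paired t-test will be performed to compare each outcome variable between active intervention group and the control group", with the Wilcoxon signed-rank test as back-up. No week or aim is attached.
- "Multiple hypothesis testing will be adjusted through" Holm's procedure. The family is not listed.
- To adjust for covariates the plan fits "a mixed effect model with a random intercept and a random slope". Its outcome "denotes the repeated average BP outcomes for subject i at occasion j". The fixed effects are an intercept, time, two intervention indicators (a2, a3) and covariates. Aim 1a is a2 = 0, Aim 2a is a3 = 0, and Aim 2b is a2 = a3.
- Power for Aim 2a is described as "comparing “bedroom alone AFU” (block 2) versus “control” (block 3) group", and Aim 2b is listed among the powered aims.

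Statistical Analyses and Data Management adds that "statistical analysis plans are provided in full in the Study Record".

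**The concern.** A model with one treatment coefficient and no treatment-by-week term cannot separate an early effect from a sustained one. The time term removes drift common to both conditions, not a change in the treatment effect. If this model decides Aim 1a, a short-lived week-1 effect can be reported as a 4-week benefit, and an effect present only in week 4 can be missed. If the paired t-test decides, the week is still open, and it could be settled after the data are seen.

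The three aim tests also describe a different trial. Testing a2, a3 and their equality needs two active conditions and a control. This trial has one active condition and one sham.

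**Working it through.** **1. Inputs.** From Study Power and Analysis Plans: n = 50, effect 3 mm Hg, SD 8.2, stated power 90.3%, paired analysis, and a sensitivity range that begins "Within the range of the SD of systolic BP measurements from 6.2 to 9.8". The alpha level is not stated; two-sided 5% is assumed. The plan does not say whether 8.2 is the SD of one measurement or of the paired difference.

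**2. The plan's own figure.** For a paired t-test, the noncentrality is 3 / (SD/√50) on 49 df. SD 8.2 gives 71.8%, not 90.3%. A power of 90.3% needs a paired SD of 6.38. If 8.2 is the SD of one measurement, that implies a within-person correlation of 1 − 6.38²/(2 × 8.2²) = 0.70, which is not stated. Both paired SDs are carried below: 6.4 (back-calculated) and 8.2 (as printed).

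**3. What the pooled coefficient estimates.** Let D1 and D4 be a person's active-minus-sham differences in weeks 1 and 4, with equal SD and correlation s. The documents do not give s, so 0 to 0.75 is assumed. The pooled estimate has mean (δ1 + δ4)/2 and SD × √((1+s)/2) per person. With δ1 = −3 and δ4 = 0 the mean is −1.5. Example: SD 8.2 and s = 0.5 give 8.2 × √0.75 = 7.10, noncentrality 1.5/(7.10/√50) = 1.49, and rejection in 31.0%.

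| Paired SD | Pooled test positive, s = 0 / 0.25 / 0.5 / 0.75 | Week-4 test positive |
|---|---|---|
| 6.4 | 63.2 / 53.8 / 46.7 / 41.2% | 5% |
| 8.2 | 43.4 / 36.1 / 31.0 / 27.3% | 5% |
| 9.8 (top of the plan's range) | 32.3 / 26.9 / 23.2 / 20.6% | 5% |

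These figures assume a correct standard error. A simulation of the plan's own mixed model at s = 0 (600 trials, Monte Carlo error about 2 points) gave 58.5% at SD 6.4 and 40.8% at SD 8.2, slightly lower.

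**4. Reverse case.** With no effect in week 1 and −3 in week 4, the pooled mean is again −1.5, so detection is the same 41-63% or 27-43%. A week-4 paired test has 90% or 72%.

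**5. What Holm does depends on its family.**

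- *Across separate week-1 and week-4 tests:* a false week-4 claim occurs in 3.9-4.6% of simulated trials.
- *Across two or three aim tests, each already pooled:* at the first step (2.5% or 1.67%), the false claim remains in 25-52% (SD 6.4) or 15-32% (SD 8.2).
- *Either week may decide and no Holm across weeks:* with no effect in either week, 8-10% of trials are positive.

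**6. Estimability.** With two conditions, the columns for intercept, time and the two indicators have rank 3 of 4 under every coding tried:

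| Coding (active / sham) | Estimable |
|---|---|
| 1 / 0 | a2 only |
| 2 / 0 | a3 only |
| 1 / 2 | a2 − a3 only |
| 2 / 3 | a3 only |

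In each row the one estimable quantity is active versus sham. Aims 1a and 2a are therefore the same comparison. Aim 2b, which needs a second active condition, has none.

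**The case against.** The strongest reply is that pooling is a literal reading and not the only one. The power text attaches a paired comparison to Aim 1a at each time period. The paired t-test is listed first, and the mixed model is introduced as the covariate-adjusted analysis. The plan never says the weeks are pooled, and it does not define the occasions. Secondary endpoints are left at nominal significance, so Holm may be meant for the primary tests. Once the duplicate and untestable aims are removed, those are week 1 and week 4, and Holm across them protects the week-4 claim. All of this stands. It shows that a sound reading exists, but no sentence selects it.

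Complete loss of a 3 mm Hg effect by week 4 is an extreme case, and partial fading would mislead less. The reverse case sits poorly with the earlier trial's 3.2 mm Hg reduction over 3 days. The figures in the working show what the literal test permits. They do not forecast this trial.

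The three-condition text looks like leftover drafting, and Specific Aims no longer lists Aim 2b. That is fair, but Table 1, the power text and the model still carry it.

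A reader might infer from the block labels in the power text (bedroom 2, control 3) that a2 has no data and Aim 1a loses its test. The documents do not support that. The model defines its index as the intervention received, not the block number, and active versus sham is estimable under every coding.

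**Conclusion.** Wrong as written, and should be fixed; confidence is moderate. The only analysis-plan test tied by name to the 4-week aim does not isolate week 4. Under the literal pooled reading, n = 50, s from 0 to 0.75 and complete fading of a 3 mm Hg effect, it is positive in 41-63% (paired SD 6.4) or 27-43% (SD 8.2) of trials, against 5% for a week-4 test. Holm applied to two weekly tests would remove the problem, but the family is not stated.

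The three aim tests cannot all be run on two conditions, and Aim 2b cannot be tested at all. This part does not depend on any assumed SD or correlation.

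A reader might go further and conclude that the trial will pool the weeks and call a transient effect a 4-week benefit. The documents do not establish this: paired weekly tests are also allowed for, and the Study Record, which may name the deciding test, is not available here.

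**What to change.** In Study Power and Analysis Plans:

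1. Replace the two indicators with one active-versus-sham indicator, and add period, week and treatment-by-week terms. Keep the listed covariates.
2. Name the week-4 active-minus-sham contrast, or more simply the week-4 paired t-test, as the single primary test of Aim 1a, and state the alpha level.
3. Report the week-1 contrast and the treatment-by-week term with confidence intervals as supporting evidence. At SD 8.2 the interaction test has only 43-95% power against complete fading of 3 mm Hg, so a non-significant result does not show persistence.
4. List the hypotheses that Holm's procedure covers.
5. Merge Aim 2a into Aim 1a. Delete a3, Aim 2b and its power claim here and in Table 1.
6. State before unblinding whether the home systolic average uses morning readings or morning and evening readings.

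A participant-by-block random intercept is optional. If the Study Record already names the deciding test, bring that text into the plan.

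**Cost.** Wording and a few lines of code; no new data. If the effect persists equally in both weeks, week 4 alone has less power than a correctly specified pooled test: 72% against 77-95% at SD 8.2, and 90% against 93-99.6% at SD 6.4. Keeping both weeks under Holm instead gives week-4 power of 66-68% or 88-89%.

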PM2.5 monitoring: Continue with in-room (PurpleAir) monitoring per original study design for full 4 weeks of both study blocks. We will use personal-PM2.5 monitoring (pDR-1500); however, it will not occur during week-1 but only at end of week-4 for both study blocks (once per study block).

Air filter intervention: No changes. We will continue the protocol using portable air cleaners (PACs) in the bedroom without change for 4 weeks in active and sham conditions.

Study flow: All study devices (home BP monitors, pDR-1500 personal PM2.5 monitors, PurpleAir in-room PM monitors, PACs) will be cleaned and sterilized (per COVID-19 protocols) before they are provided to each subject. The devices will be provided to the subjects without any contact with the research team members. At the appropriate time in the protocol, the subjects will be notified by phone and the equipment and instructions for usage and set up will be dropped off for the participants at their doorway at a pre-arranged time.

Advanced Covid Restrictions:

Study staff will not enter residences or have any personal contact with any subject or potential subject. In the event of elevated Covid concerns the study staff will not enter hallways and will deliver equipment to the front doorway to Carpenter Place. In cases where the subject agrees, the study staff may enter apartments to set up the equipment. Our 2021 experience has proven that some subjects have physical limitations to moving the equipment (frailty, walkers and small apartments, etc)

Study Protocol:

Recruitment: Advertisements and recruitment will be done without personal contact. We will provide fliers for recruitment with a contact number to the research coordinator for interested residents. The staff members who work and are present at Carpenter Place will post the fliers in Carpenter place bulletin boards and notify residents that the study is active and has been modified to be simpler and to eliminate any contact with the research team. Advertisements will continue in the residential newsletter.

Enrollment: Interested residents will call the study research coordinator. Study inclusion/exclusion criteria will be reviewed (no changes). All subjects must attest to be non-smokers living in non-smoking household. Consents will be left at the office or subjects will be emailed or mailed the consent form and subjects will be given ample time to review the consent and consider their participation independently. Study team will review the consent document over the telephone just as they would during a face to face meeting. Signature will be obtained on the consent form and provided to the study staff via mail or left for pickup by study staff in the same manner as equipment is dropped off with no contact. This cohort is unlikely to benefit from electronic consenting procedures based on the lack of internet access, the poor internet provided by Carpenter Place, the willingness of the participants, and the added burden it would place on this older population of subjects participating in a low risk study.

Study Flow: The modified trial will be conducted per the original design except for no face-to-face interactions between research staff and subjects and the protocol has been simplified. Subjects will be assigned a research ID number. They will be randomized in a blinded fashion to either active vs sham PAC use for intervention block 1. After completing block 1, they will washout for 1 week and then crossover to block 2 and undergo the same trial randomized to the alternative PAC intervention (sham vs active).

BLOCK 1 (2)													Washout	
	Week 1 (6)					Wk 2-3 (7-8)		Week 4 (9)						
	Day					Day								
	1 M	2 T	3 W	4 Th	5 F			1 M	2 T	3 W	4 Th	5 F		
PAC INTERVENTION (2 limb x-over)														
Randomized PAC	↓	x	x	x	x	----->	x	x	x	x	x	↑		
TESTING														
Home BP: AM		✓	✓	✓	✓			✓	✓	✓	✓	✓		
PM		✓	✓	✓	✓			✓	✓	✓	✓	✓		
PM MONITORING														
In-room PM (Purple Air)	↓	x	x	x	x	----->	x	x	x	x	x	↑		
Personal PM (PDR1500)											↓	↑		

↓ = start; x = continue; ↑ = stop; ✓ = check BP; -----> = continues throughout period

Week-1/day-1: PAC Intervention/bedroom PM monitoring: Start in subject's bedroom at 9 am

Home BP: am= when first wake up in bedroom; pm=just before going to sleep in bedroom

Personal PM monitoring: Wear/have on person during daytime. Put by bedside at night-time.

Week-1/day-1: Staff will drop off the study equipment between 8-9 AM. The equipment will all have been cleaned and sterilized beforehand. It includes a home BP monitor (and instructions), the blinded-randomized (active or sham) indoor PAC (and instructions for its use), and a PurpleAir monitor (and instructions for positioning and use).

At 9 AM, the subject will position the PAC in their bedroom per instructions, plug it in and turn it on. They will keep the PAC running at the highest tolerated setting (per protocol and instructions) and keep it running throughout weeks 1-4 in their bedroom. The subject will also plug in the PurpleAir and position it at least 6 feet away from the PAC in their bedroom per instructions (off the floor on a table). They will make sure it is running for continued air pollution monitoring throughout weeks 1-4 in their bedroom per provided instructions.

Home BP monitoring: The subject will measure home BP upon awakening in the morning and just before bedtime on week-1 (days 2-5 = Tuesday through Friday) and on week-4 (days 2-5 = Tuesday through Friday). They will follow instructions for home BP monitoring without change from original protocol. They will sit 5 minutes prior to measurement with right arm resting at heart level on a table. They will measure BP in triplicate on right arm. The Omron-10 series will be set to measure BP in triplicate at 1-minute intervals. The device stores all time-stamped BP readings and subjects will record on a log for safekeeping of data.

Subject reminders: The study coordinator will contact the subject week-4/day-1 (mon) to remind the subject to begin home BP monitoring on week-4/day-2 for the next 4 days.

Personal PM-monitoring (week 4): The study coordinator will call the subjects and Carpenter Place staff to remind them about personal PM monitoring which will occur on week-4/day-4 starting at 9-AM and continue for 24-hours through day-5 at 9-AM. The coordinator will drop off the pDR-1500 (with instructions for use) before 9-AM on day-4 at the front lobby of Carpenter Place. The subject will pick-up the monitor, turn it on, and wear it (on belt or strap) for the next 24-hours as per instructions. During sleep or showering the monitor can be kept close to their person (bedside).

Week-4/Day-5: On the final day of each study block, the coordinator will contact the subject. They subject will be instructed to place the equipment (randomized PAC, PurpleAir, pDR-1500, and home BP device) in the bin with wheels and bring it to the front lobby of Carpenter Place. The coordinator will then pick-up the equipment.

Data collection: The coordinator will collect/data-base the time-stamped home BP readings from week-1 and week-4. They will download all the time/date-stamped PM2.5 data from the PurpleAir and data-base the results. They will also download and data-base the 24-hour personal PM2.5 exposure results from the pDR-1500.

As-needed visits: During the study period, the subject can call and schedule an as-needed telephone or video visit with the research coordinator at any time to discuss any study-related issues or problems.

Washout-period. During the washout period the coordinator will clean and sterilize all the equipment. They will change the PAC to the alternative randomized blinded mode (active vs sham). They will call the subject and schedule the timeline for Block-2 (week-1/visit-1).

Block-2: This block will proceed exactly as block-1, except the subject will be provided the alternative randomized (blinded) PAC intervention.

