Week 1/day 1: An investigator will place one AFU in the bedroom of each participant's apartment. Each AFU will be set to either "active mode" (i.e., a HEPA filter inside) or "sham mode" (i.e., no HEPA filter inside) in **randomized double-blind fashion**. We have documented that both modes exhibit similar noise and identical appearance. This will be accomplished by having a different (unblinded) investigator set the AFU modes offsite beforehand – so that neither the on-site investigator nor the participants will be aware of the settings during all study blocks. This offsite unblinded investigator will be the only team member aware of the randomization order. For the **placebo intervention**: both AFUs will be set to "sham mode". The AFUs will remain running in the same mode for the entire 4-week study block.

Week 1/days 2-4: Participants will be asked to sleep every night in their own apartment and measure their blood pressure using a home BP device we provide just prior to going to bed and upon waking up. At the end of the visit on day 4, participants will have heart rate variability determined with a holter monitor for 6 minutes and blood pressure measured using the BPTru device. Subjects will be fitted with 2 portable devices: an ambulatory BP monitor and a personal PM2.5 monitor. At all times during the 24-hour period, they will wear the PM monitor or have it near them (e.g., on bedside stand while sleeping). We have demonstrated that these devices can be worn together for 24 hours without excessive burden^{38,40}. During this period, participants will be instructed not to exercise.

Week 1/day 5: Upon arrival the personal monitoring devices will be collected.

Weeks 2-3: Participants will undertake their usual activities (except for overnight travel restrictions).

Week 4: Study visit days 2-5 will be repeated as during week 1.

Visit day 5 is completed and prior to eating or taking medications, participants will have blood drawn in the study room by an investigator. An investigator will then remove the AFUs from participants' apartments.

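### The coordinator has unmasked access to Block 1 PM2.5 data, which are informative about the Block 2 mode, and no safeguard is stated even if someone else swaps the filter

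*Combined protocol and SAP*

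**What the plan says.** The main protocol (Block 1, Week 1/day 1) describes a double-blind set-up in which a separate offsite investigator sets the units: "This offsite unblinded investigator will be the only team member aware of the randomization order". The AFU intervention section has that investigator fit or remove the filters during washout. The later Protocol Modifications (Study Flow) keep the original design apart from removing contact and simplifying the protocol. They assign each participant to the alternative mode in Block 2.

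The Protocol Modifications then give the following tasks to the coordinator. The text says coordinator, study coordinator and research coordinator, apparently for one role.

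- End of block (Week-4/Day-5): "The coordinator will then pick-up the equipment".
- BP outcome data: "The coordinator will collect/data-base the time-stamped home BP readings from week-1 and week-4".
- Bedroom PM2.5: "They will download all the time/date-stamped PM2.5 data from the PurpleAir and data-base the results".
- Personal PM2.5: "They will also download and data-base the 24-hour personal PM2.5 exposure results from the pDR-1500".
- Contact: week-4 reminder calls, the washout call that schedules Block 2, and unscheduled contacts, since "the subject can call and schedule an as-needed telephone or video visit with the research coordinator at any time".
- Washout, where the subject is still the coordinator: "They will change the PAC to the alternative randomized blinded mode (active vs sham".

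No passage masks the PM2.5 values, delays access to them, or gives them to anyone else.

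**The concern.** PM2.5 is what the intervention changes, so a PM2.5 record carries information about the mode that produced it. The PurpleAir sensor stands in the same bedroom as the unit. With two modes and one block of each, a correct guess about Block 1 is also a correct guess about Block 2.

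The person holding these values then deals with the participant in Block 2 and databases the BP outcome. What is at stake is the promise that staff in contact with participants do not know the order. Unequal handling could enter through encouragement to keep the unit running, through data queries, or through application of the rule that removes participants who spend more than 4 days of a block offsite (Activity restrictions). This route does not depend on who swaps the filter, so moving that task offsite would leave it open.

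**Working it through.** **Size of the signal.** The plan's own figure comes first. Specific Aims gives a 42% fall in personal PM2.5 in RAPIDS, and 1 − 9.1/15.7 = 0.420. The Progress Report gives 10.9 and 7.4 µg/m³ for the two active filters, with mean 9.15, and 1 − 9.15/15.7 = 0.417. The figure reproduces. Other inputs from the documents:

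- 30–50% reduction across AFU trials (Specific Aims).
- RAPIDS living room, sham to high-efficiency: 1 − 7.0/17.5 = 60%.
- RAPIDS personal, sham to high-efficiency: 1 − 7.4/15.7 = 53%.

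**Spread between apartments.** The documents give no SD for block-average bedroom PM2.5 under one mode, so it is assumed. The only site figure is outdoor (Pollutant levels): mean 16.6, SD 10.7. This gives CV = 10.7/16.6 = 0.645 and, if lognormal, log-SD = √ln(1 + 0.645²) = 0.589. It is a proxy. The working range is log-SD 0.4 to 0.8.

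**Formula.** For lognormal values with equal log-SD *s* in both modes and equal numbers per sequence, the best guess from one block average is right with probability Φ(−ln(1 − reduction) / (2*s*)). Example: 60% reduction, *s* = 0.4: 0.916/0.8 = 1.145, Φ = 0.874.

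| Reduction | *s* = 0.4 | *s* = 0.589 | *s* = 0.8 |
|---|---|---|---|
| 30% | 67% | 62% | 59% |
| 42% | 75% | 68% | 63% |
| 50% | 81% | 72% | 67% |
| 53% | 83% | 74% | 68% |
| 60% | 87% | 78% | 72% |

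Chance is 50%. If apartments differed much less (*s* = 0.2), the rates for 30% to 60% reductions would be 81% to 99%.

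**How often is the guess near-certain?** The share of participants whose mode could be correctly called with at least 95% certainty is, at *s* = 0.4, 0.589 and 0.8 respectively:

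- 42% reduction: 6.9%, 0.3% and 0.0%.
- 60% reduction: 44%, 13% and 2.3%.

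**Timing.** The equipment is collected on the last day of the block, so nothing is learned by this route during Block 1. The Data collection paragraph sits between the Day-5 pick-up and the washout, which suggests that the download precedes Block 2. No date is stated.

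**The case against.** The strongest objection is that, as written, this route adds nothing: the washout paragraph already has the coordinator change the mode, and whoever fits or removes a filter knows the mode outright. That is correct for the current text. The point still matters, because someone who returned only the filter swap to the offsite investigator could believe the blind restored while the sensor data remained open.

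A reader might also infer that Block 1 data reveal both modes and that the staff blind fails. The documents do not support that. Before Block 2 there is one block per participant and no within-person comparison. Windows and cooking are unrestricted. The 60% and 53% figures come from two units over 3 days, whereas this trial runs one unit at whatever speed the participant tolerates. With the outdoor SD and 30–50% reductions, the guess is right in only 62–72%. Nor is it stated that the coordinator reads or compares the values. In the other direction, a four-week average from a sensor in the filter's own room, and experience gained from participants who have finished, could sharpen the guess.

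A reader might further infer biased BP results. This route does not unblind participants. They take their own readings in triplicate on an automated device that stores time-stamped values, and Block 2 is meant to run as Block 1 did. This objection largely stands. The topics of the as-needed calls are not specified beyond study-related matters, so a link to BP technique is conjecture.

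**Conclusion.** The concern holds in limited form. One role has unmasked access to Block 1 PM2.5 data, apparently before Block 2, together with the BP database and participant contact. Those data are informative about the Block 2 mode: a best guess is right in about 59–87% of participants, against 50% by chance. That range rests on reductions of 30–60%, an assumed log-SD of 0.4–0.8, lognormal values with equal spread in both modes, and access before Block 2.

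The right description is that the staff blind is not protected by this data flow, whoever swaps the filter. The likely effect on BP is small, and no path to a BP difference has been quantified. This is an inexpensive improvement that supports the double-blind claim, not a defect that undermines the primary comparison.

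**What to change.** Have a team member with no participant contact and no BP-data role download and hold the PurpleAir and pDR-1500 files after each block. The offsite unblinded investigator could do this, limited to the download and a working/not-working check. That limit matters because indoor and personal PM2.5 are listed as primary exposure outcomes in Table 1, and someone who knows the allocation should not be judging those values. Release no PM2.5 values to the coordinator or the participant until that participant's Block 2 BP data are locked, and state when the download takes place. The coordinator keeps the BP data and the calls.

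In the same amendment, reconcile the washout paragraph, where the coordinator changes the mode, with the main protocol, where the offsite investigator does. Without that, the PM2.5 change alone does not restore the staff blind.

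The cost is one reassigned task, with no new staff or visits. The downside is that the coordinator learns of sensor faults only as working or not working.
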